2.2 Design Summary

This will be a non-randomized, multicenter, prospective study conducted at up to forty-five (45) Clinical Investigative Sites (referred to as "Sites" in the remainder of this document), with up to 40 sites in the U.S and up to 5 sites in Japan with the objective of determining whether the TBE device is safe and effective in treating lesions of the aortic arch and descending thoracic aorta. A minimum of 175 and up to a total of 465 Subjects will be enrolled across four independent study arms consisting of seven cohorts as described below. The anatomically suitable non-aneurysm cohorts will be referred to as the Non-Aneurysm Lesion (NAL) Cohorts.

The study will consist of seven cohorts described as follows:

- Zone 2, aneurysm patients (N=115, maximum)
 - Zone 2, aneurysm patients, Primary Enrollment (N=85)
 - Zone 2, aneurysm patients, Continued Access Enrollment (N=30, maximum)
- Zone 2, anatomically suitable non-aneurysm patients, descriptive analysis (N=200, maximum)
 - Dissection cohort (N=20 minimum)
 - Traumatic Transection cohort (N=10 minimum)
 - Other isolated lesion types cohort (No minimum)
- Zone 0/1, aneurysm patients, hypothesis driven (N=50, 0-10 Subjects from Japan) NOTE: due to removal of the 49/53mm device sizes from this trial, any Subjects enrolled with these device sizes will not be counted as part of this N=50 enrollment and replacement Subjects will be enrolled to keep N=50)
- Zone 0/1, anatomically suitable non-aneurysm patients, descriptive analysis (N=100, maximum)

CONFIDENTIAL INFORMATION

- Dissection cohort (N=10 minimum)
- Other isolated lesion types cohort (No minimum)

The Zone 2 aneurysm cohort will consist of 85 subjects accrued during the Primary Enrollment period along with a maximum of 30 subjects accrued during the Continued Access Enrollment period. Any Zone 2 training cases enrolled from Japan would not be included in PMA analysis, nor do they count towards enrollment minimums/maximums as shown above. However, once enrolled, the Japan Zone 2 training cases may be included for some analysis.

The maximum number of Subjects that may be enrolled at a single site is as follows:

- Zone 2, aneurysm patients, 17 Subjects
- Zone 0/1, aneurysm patients, 8 Subjects in US, 4 Subjects in Japan
- Zone 2 and Zone 0/1, anatomically suitable non-aneurysm patients, all cohorts, will not have a maximum per site as they are for descriptive analysis only

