2.3.1.1 Zone 2 Aneurysm Cohort

The Primary Endpoint for the Zone 2 aneurysm cohort will be a composite of the following events through 12 months (through day 546 unless otherwise specified in study protocol component definitions) following the index endovascular procedure:

- Device Technical Success
- Absence of the following:
 - Aortic rupture;
 - Lesion-related mortality;
 - Disabling stroke
 - Permanent paraplegia
 - Permanent paraparesis
 - New onset renal failure requiring permanent dialysis
 - Additional unanticipated post-procedural surgical or interventional procedure related to the device, procedure, or withdrawal of the delivery system.
- 2.3.1.2 Zone 0/1 Aneurysm Cohort

[figure not shown]
The Primary Endpoint for the Zone 0/1 aneurysm cohort will be Strategy Success.

Strategy Success (For planned staged procedures – landing zone optimization, transposition, and device placement – through one month following last planned procedure) and is defined as follows: a composite of the following events from the time of enrollment through one month following the index endovascular procedure (through day 59 unless otherwise specified in study protocol component definitions):

[figure not shown]
- Initiation of the index endovascular procedure following the debranching procedure
- Device technical success for the index endovascular procedure
- Absence of the following :
 - Aortic rupture
 - Lesion-related mortality
 - o Disabling Stroke
 - Permanent paraplegia
 - Permanent paraparesis
 - New onset renal failure requiring permanent dialysis

GORE CONFIDENTIAL INFORMATION

 Additional unanticipated post-procedural surgical or interventional procedure related to the device, procedure, or withdrawal of the delivery system.

GORE CONFIDENTIAL INFORMATION

2.4 **Statistical Hypotheses**

- 2.4.1 Performance Goal Derivation
 - 2.4.1.1 Zone 2 Aneurysm Cohort

Historical TAG/CTAG results (TAG 99-01, TAG 03-03, TAG 04-02, TAG 05-02, TAG 08-03) were re-analyzed to determine the Zone 2 aneurysm cohort performance goal for the Primary Endpoint (see study protocol for this data). Subjects treated for DTA aneurysms with proximal device placement in Zone 2

GORE CONFIDENTIAL INFORMATION

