2.4.1.2 Zone 0/1 Aneurysm Cohort

A systematic literature review of hybrid repair literature was conducted (see study protocol for in-depth description of this literature review). Key results that were consistently identifiable from the review included perioperative death, neurological events and spinal cord ischemia, all of which are part of the Zone 0/1 Primary Endpoint. The results were individually summarized (i.e., a rate for each outcome was calculated across the identified literature) and then summed up; the estimated total percent of these events was 23.6%. Additional events included in the Primary Endpoint of the Zone 0/1 statistical arm are renal failure and the components of technical success. To account for these additional factors, an adjustment of 11% to the overall point estimate from the literature analysis was employed, increasing the anticipated point estimate from historical results to 34.6%. To account for potential variability in the new study population an additional margin of 5% was incorporated. This additional adjustment to the performance goal is justified given the potential for underreporting of key events in literature and national databases. Due to this consideration, the study performance goal (success) for the proposed Zone 0/1 Primary Endpoint was set at 60%.

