2.4.3 Zone 0/1 Aneurysm Cohort Hypothesis

The analysis of the Primary Endpoint for this cohort is intended to test the hypothesis that the success exceeds the performance goal of 60%. Using the performance goal of 60% with Primary Endpoint success through one month, the following hypothesis will be tested:

To meet the performance goal

of 60%, a point estimate of > 74% Primary Endpoint success for 50 patients through one month is required. No attrition was accounted for.

Sample size calculations were determined using PASS 13 one-sided exact test for one proportion.

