5.1.1.2 Zone 0/1 Aneurysm Cohort

The composite Primary Endpoint analysis population (to test the hypothesis) for the Zone 0/1 aneurysm cohort will be among enrolled Subjects (excluding those with a CEC adjudicated 'major' inclusion/exclusion criteria violation or FDA mandated exclusion) and is outlined as follows based on events as described in Section 2.3.1.2:

- Subjects with an event any time \leq 59 days are a failure regardless of whether they had imaging in one month window
- Subjects that don't have imaging in the one month window and don't have an event \leq 59 days are excluded
- Subjects with imaging in one month window and no event reported \leq 59 days are successes
- Subjects with >1 event just count once as failures

The analysis population for the Zone 0/1 Aneurysm cohort will also exclude any Subjects treated with a 49/53mm device since those device sizes have been removed from this study. Any Subjects enrolled and treated with those device sizes will not be counted in the N=50 enrollment and replacement Subjects will be enrolled to keep N=50. The 49/53mm Subjects will be summarized separately and followed per the Protocol.

This analysis will also be repeated with 12 month results (following the same analysis population logic as that outlined for the Zone 2 aneurysm cohort in Section 5.1.1.1) with the exception that no hypothesis will be tested.

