5.3 Primary Endpoint Analysis

5.3.1 Zone 2 and Zone 0/1 Aneurysm Cohorts

The proportion of composite Primary Endpoint success (1 - composite Primary Endpoint failure) will be calculated for each hypothesis-driven cohort based on the details outlined for each Primary Endpoint component in **Appendix A**. One-sided Exact confidence intervals for binomial proportions (alpha=0.05) will be constructed to test each calculated composite proportion against the respective Primary Endpoint hypothesis. Each hypothesis-driven cohort tested must meet their respective Primary Endpoint analysis population criteria. The null hypothesis will be rejected if the lower bound of the 95% confidence interval estimating composite Primary Endpoint success exceeds the performance goal.

In addition, the Primary Endpoint data (composite and components) for each of these two cohorts will be summarized by statistics (count and percent).

In order to assess the impact of missing data on each of the composite Primary Endpoint hypothesis tests, sensitivity analyses will be performed and are outlined in **Section 5.5.1**.

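### The Zone 0/1 test population drops 49/53mm subjects by device received, but the N=50 count drops them by device at enrollment, so failures before implantation fall between the two rules

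*SAP*

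**What the plan says.** **Enrollment count.** The notes on the Zone 0/1 aneurysm cohort in SAP sections 2.2 and 3.1 say that "any Subjects enrolled with these device sizes will not be counted as part of this N=50 enrollment" and that replacements will be enrolled. Neither section defines what being enrolled with a size means.

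**Analysis population.** Section 5.1.1.2 starts from enrolled subjects. It counts any event up to day 59 as a failure, with or without imaging, and then adds: "The analysis population for the Zone 0/1 Aneurysm cohort will also exclude any Subjects treated with a 49/53mm device". Its own replacement sentence requires the subject to have been both enrolled and treated with the size. It promises a separate summary of the 49/53mm subjects. It also removes subjects under an FDA-mandated exclusion, which the supplied text does not define.

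**Endpoint.** Section 2.3.1.2 defines Strategy Success as "a composite of the following events from the time of enrollment through one month following the index endovascular procedure". Starting the index endovascular procedure after debranching is a component. Appendix A scores it as failed when the site records that the subject did not continue. The Protocol Summary allows up to 60 days between the two phases.

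**Twelve-month repeat.** Section 5.1.1.2 has the analysis repeated at 12 months, "following the same analysis population logic as that outlined for the Zone 2 aneurysm cohort in Section 5.1.1.1". Section 5.1.1.1 contains no device-size exclusion.

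**The concern.** The sponsor withdrew two device sizes and wants the test to describe the remaining ones. That calls for removing a type of subject, identified before outcomes occur. Section 5.1.1.2 identifies them by the device they were treated with, which is known only once Phase 2 has taken place.

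In a staged strategy this matters. A subject planned for 49/53mm may have a disabling stroke or lesion-related death after debranching, or may never start Phase 2. That subject was never treated with the device, so the exclusion does not apply and the subject counts as a failure. A subject with the same plan who reaches implantation is removed, success or failure. Membership in the confirmatory test then depends on an event that is itself part of the endpoint. The enrolled-with wording in sections 2.2 and 3.1 could remove both subjects.

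A third case has no stated class: a 49/53mm device is attempted but not delivered. Appendix A makes failed access and delivery a technical-success failure, but the SAP does not say whether such a subject was treated with the device. In a single-arm study, that decision could be left until the outcome is known.

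**Working it through.** **1. The two rules side by side, for a subject planned for 49/53mm**

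| Course after enrollment | Sections 2.2 and 3.1, read as planned size | Section 5.1.1.2, read literally |
|---|---|---|
| Event before Phase 2, or Phase 2 never started | Not counted, replaced | Stays in as a failure |
| Receives the 49/53mm device | Not counted, replaced | Removed, whatever the outcome |
| 49/53mm attempted, not delivered | Not counted, replaced | Not stated |
| Given another size | Not counted, replaced | Stays in, success or failure |

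The rules agree only in the second row.

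**2. Reproducing the plan's threshold**

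Inputs:
- Performance goal 60% (section 2.4.1.2) and n = 50.
- Test (section 5.3.1): "One-sided Exact confidence intervals for binomial proportions (alpha=0.05) will be constructed". H0 is rejected when the lower bound exceeds the goal.

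Formula: the smallest r with P(X ≥ r | n = 50, p = 0.60) ≤ 0.05, checked against the one-sided 95% Clopper-Pearson lower bound.

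- r = 37 (74%): tail probability 0.028, lower bound 0.619. Passes.
- r = 36 (72%): tail probability 0.054, lower bound 0.597. Fails.

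This matches the plan's statement that "a point estimate of > 74% Primary Endpoint success for 50 patients through one month is required", if it is read as at least 74%. Taken strictly, more than 74% would mean 38/50, one subject more than the section 5.3.1 rule needs.

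**3. Effect of retained failures, compared with exclusion by planned size**

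Let k be the number of subjects planned for 49/53mm who fail before implantation and stay in. The documents do not give k, so it is an assumption here. The true success rate of the other subjects is assumed to be 80%, because the visible text gives no design rate.

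*(a) The k failures sit inside N=50.* This follows if the 5.1.1.2 replacement sentence governs, since these subjects were not treated with the size and are not replaced. The remaining 50 − k subjects must supply 37 successes.

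Power = P(X ≥ 37 | 50 − k, 0.80). Attained alpha = P(X ≥ 37 | 50 − k, 0.60).

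| k | Power at 80% | Attained alpha |
|---|---|---|
| 0 | 0.889 | 0.0280 |
| 1 | 0.834 | 0.0171 |
| 2 | 0.759 | 0.0098 |
| 3 | 0.667 | 0.0053 |

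Each such failure takes one of 50 places, or 2 percentage points (1/50), from the highest attainable success rate.

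*(b) The k failures are additional to 50 others.* This follows if 2.2 governs the count and 5.1.1.2 the analysis. Then n = 50 + k, and the 50 others must supply the minimum r for that n.

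| k | Needed | Power at 80% |
|---|---|---|
| 1 | 37/51 | 0.889 |
| 2 | 38/52 | 0.814 |
| 3 | 39/53 | 0.711 |

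With k = 1 nothing is lost: 37/51 still passes (lower bound 0.605). With k = 2, 37/52 fails (lower bound 0.591).

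**4. Compared with including every 49/53mm subject**

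Excluding implanted subjects removes their successes and their failures alike. The sign of the net effect depends on outcomes that the documents do not give.

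**The case against.** The strongest reply is that this is a small wording mismatch that works against the sponsor. Much of that stands.

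- **Direction.** A reader might infer that a rule depending on outcome flatters the device. The documents do not support that. Against exclusion by planned size, the only subjects who stay in because they were never implanted are failures. Success is biased downward and attained alpha falls.
- **Count.** The number of 49/53mm subjects is not given, and the number who failed before implantation may be zero. Any probability that the rules classify someone differently would rest on invented counts. It would also not be the probability that the conclusion changes, which requires a result at the boundary. That one subject can separate pass from fail at 37/50 is true of any exact binomial threshold.
- **Other text.** The undefined FDA-mandated exclusion might already remove these subjects. Section 4.0 refers the enrollment definition to the protocol, of which only the summary is supplied. Section 5.1.1.2 may be meant as the operative definition, with 2.2 and 3.1 describing enrollment only.
- **Twelve-month repeat.** A reader might infer that the one-month and 12-month results will describe different populations. That is only one reading. The exclusion is worded for the cohort's analysis population generally, and the reference to 5.1.1.1 may supply only event and imaging logic. The text is unclear, not contradictory.
- **Visibility.** A reader might infer that the effect of the exclusion will be hidden. Section 5.1.1.2 promises a separate summary of these subjects, although its content is not specified. The body of section 5.5.1 on sensitivity analyses is not in the supplied text, so the absence of an inclusive analysis cannot be established.

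The reply does not remove the mismatch. Two rules that are not equivalent decide who is counted and who is tested in a hypothesis test, and one of them turns on an event after enrollment.

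**Conclusion.** The point holds as an inconsistency that should be settled before the Zone 0/1 primary analysis. Read literally, section 5.1.1.2 keeps pre-implant failures among subjects planned for 49/53mm and removes those who received the device. Sections 2.2 and 3.1 use a different criterion, and an attempted but undelivered device is left unclassified.

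The cost against a planned-size rule is power, not false positives. It ranges from nothing (one failure additional to 50 others) to a fall from 0.889 to 0.667 (three failures inside N=50). These figures assume an 80% true success rate and the stated values of k. If k is zero, this mechanism has no effect. Against a population that includes all 49/53mm subjects, the direction cannot be determined from the documents.

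**What to change.** 1. Use one exclusion rule in sections 2.2, 3.1 and 5.1.1.2, for both the N=50 count and the analysis population. Base it on the aortic component size planned before the endpoint clock starts, and apply it whether or not implantation was attempted or completed. Section 4.1 lists a Case Planning form, but its fields are not shown, so the sponsor should confirm that it records planned size and that it is completed in time.
2. State that the same rule covers the Zone 0/1 12-month repeat.
3. State whether the FDA-mandated exclusion reaches any of these subjects.
4. Report one supportive Zone 0/1 Strategy Success result with all enrolled 49/53mm subjects included, beside the separate summary already promised.

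The cost is SAP wording and one table row; the design and sample size do not change. There are two downsides. A subject planned for another size but given 49/53mm would stay in the primary test and should be listed. The inclusive figure may also be less favourable than the primary one.

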5.1.1.3 NAL Cohorts

[figure not shown]
No hypotheses will be tested for any of the NAL cohorts. An NAL cohort will be summarized separately if there are at least 10 Subjects for a cohort. Else, NAL Subjects may be grouped by Zone (Zone 0/1, Zone 2) for analysis instead.

The Primary Endpoint analysis population for each of the five NAL cohorts will be among all enrolled Subjects (excluding those with a CEC adjudicated 'major' inclusion/exclusion criteria violation or FDA mandated exclusion). In addition, the Primary Endpoint analysis population for each NAL cohort will follow Zonesimilar logic to that written for the two hypothesis-driven aneurysm test arms (as described above in Section 5.1.1.1 (Zone 2) and Section 5.1.1.2 (Zone 0/1)).

[figure not shown]

GORE CONFIDENTIAL INFORMATION

However, additional analysis may be done with different analysis population criteria.

5.1.3 Additional Analyses

The analysis population for all other analyses (outlined in **Section 5.5**) for each of the cohorts will be among enrolled Subjects (excluding those with a CEC adjudicated 'major' inclusion/exclusion criteria violation or FDA mandated exclusion). Any additional analysis population details are outlined in the appropriate subsection of **Section 5.5**.

5.2 **Timing of Analyses**

Prior to primary analysis, the composite Primary Endpoint results

will not be analyzed (except as detailed below in Section 5.2.2) for the two hypothesis-driven test arms. Serial analyses of long-term results will occur during the follow-up period. A final analysis will be conducted once study follow-up is complete. In addition to the Primary Endpoint at primary analysis time points, all other additional analyses (detailed in Section 5.5) will also be performed.

Details on primary analysis timing are provided in the below subsequent sections:

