5.1 Analysis Populations

- 5.1.1 Primary Endpoint
 - 5.1.1.1 Zone 2 Aneurysm Cohort

The composite Primary Endpoint analysis population (to test the hypothesis) for the Zone 2 aneurysm cohort will be among enrolled Subjects (excluding those with a CEC adjudicated 'major' inclusion/exclusion criteria violation or FDA mandated exclusion) and is outlined as follows based on events described in **Section 2.3.1.1**:

- 1) Subjects with an event any time ≤ 546 days are a failure regardless of whether they had imaging in 12 month window
- Subjects that don't have imaging in the 12 month window and don't have an event ≤ 546 days are excluded
- Subjects with imaging in 12 month window and no event reported ≤ 546 days are successes
- 4) Subjects with >1 event just count once as failures

The rate (composite Primary Endpoint) within an analysis window (except for Procedure window) will use similar logic to that through 12 month window but will be window-dependent (i.e. 6 Month Primary Endpoint composite rate will be among those with an event in the 6 month window or had imaging in the 6 month window). All enrolled Subjects with no 'major' inclusion/exclusion criteria will be in the denominator in the Procedure window.

GORE CONFIDENTIAL INFORMATION

All hypothesis testing and Primary Analysis for the PMA will be based on Zone 2 Aneurysm Subjects accrued during the Primary Enrollment Period. Zone 2 Aneurysm Subjects accrued during Continued Access Enrollment will be analyzed separately for the PMA. Continued Access Enrollment Subjects may be pooled with the Primary Enrollment Subjects in subsequent reports and/or analysis.

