5.5.4 Adverse Events

Adverse events (AEs) will be summarized for main reporting efforts. Adverse events are defined as any untoward medical occurrences in a Subject whether device-related or not. All AEs will be recorded on the appropriate CRF and documented in the Subject's permanent medical record. The Investigator at each Site is ultimately responsible for reporting all AEs to the Sponsor, as well as to the IRB, as applicable.

Adverse events will be summarized by incidence (i.e. a specific AE will not be counted more than once for a Subject within each window) in each analysis time window using MedDRA coded terminology. Analysis time windows will begin with the initial endovascular treatment window for all cohorts; AEs with onset prior to endovascular treatment (Zone 0/1 cohorts only) will be summarized separately. The denominator for each window will be calculated as the number of Subjects remaining in follow-up as of the beginning of the analysis window. At a minimum, separate summaries by severity (serious, non-serious) will be prepared. If summaries are prepared by relationship, the following categories will be considered as related to device/procedure: related to device, related to device and endovascular procedure, or related to endovascular procedure.

Partial dates (month and/or day unknown) for AE onset and AE resolution dates will be allowed for AE analysis time window determination. Exact imputation logic will be documented in the appropriate specifications document. In general, partial dates will be imputed to be most conservative with regard to timing after initial endovascular procedure date.

Candidate AEs for Primary Endpoint and Success Outcomes will be reviewed by the independent CEC and adjudicated (outlined in Appendix A).

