5.5.4.1.3 Adverse Event Reporting and Coding

AEs will be reported on the appropriate CRF and documented in the Subject's permanent medical record. The Investigator at each Site is ultimately responsible for reporting AEs to the Sponsor.

The following information on each reported Adverse Event will be collected:

- Adverse Event Name •
- Adverse Event Onset Date •
- Relationship
- Classification (Serious or Non-Serious) •
- Treatment
- Outcome
- **Resolution Date**

Adverse Events will be coded using the Medical Dictionary for Regulatory Activities (MedDRA).

Adverse Event submission guidelines:

- Adverse Event reporting begins once the patient is enrolled in the study. All Adverse Events should be reported from enrollment through study completion / discontinuation.
- Provide a diagnosis if possible. If unable to provide a • diagnosis, report the symptoms as separate events. Adverse Events should be reported using the full name without abbreviations or narratives.
- Adverse Events with an outcome status of "Ongoing" • should be assessed at each follow-up evaluation to determine if the event has resolved. Adverse Events ongoing at study completion / discontinuation should be left as "Ongoing" on the AE case report form.

GORE CONFIDENTIAL INFORMATION

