5.5.6 Mortality

For additional analysis of all-cause mortality (in addition to Success Outcomes), Kaplan Meier methodology will be used. Subjects without death reported before the end of the time period of

GORE CONFIDENTIAL INFORMATION

interest will be censored at the Subject's last reported contact date or the end of the time period of interest, whichever date is earlier.

For additional analysis of lesion-related mortality (in addition to Primary Endpoint and Success Outcomes), Kaplan Meier methodology will be used. Subjects without a lesion-related death reported before the end of the time period of interest will be censored at the Subject's last reported contact date or the end of the time period of interest, whichever date is earlier.

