5.5.7 Reinterventions

A Site-reported reintervention will be counted as occurring if the Site reports a 'yes' to the question "Was reintervention on the treated segment of the branch vessel or the aorta performed?" from the AE CRF. The incidence of Site-reported reinterventions will be summarized by analysis time window among those remaining in follow-up. In addition, the time to first Site-reported reintervention will be calculated using Kaplan Meier methodology. Subjects without a Site-reported reintervention reported before the end of the time period of interest will be censored at the Subject's last reported contact date or the end of the time period of interest, whichever date is earlier.

Unanticipated additional procedures related to the device, procedure, or withdrawal of the delivery system (meeting Primary Endpoint or Success Outcome criteria) will be summarized in the Primary Endpoint and Success Outcome tables and are not reconciled with Site-reported reinterventions as described above.

Initially treated Zone 2 cohort Subjects that have a reported reintervention involving Zone 0/1 treatment will remain in their original enrolled cohort for statistical analysis but narratives will be provided on these Subjects in submissions to the FDA (in all appropriate sections of the submitted report). In addition, the number and percent of these Subjects will be summarized.

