5.5.8 Stroke and Paraparesis/Paraplegia

For additional analysis of these events (in addition to Primary Endpoint and Success Outcomes), all Subjects remaining in follow-up will be part of this analysis population. Event rates of each type of event will be displayed separately as well as an overall rate.

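### SAP 5.1.3 leaves subjects with a major eligibility violation or an FDA mandated exclusion out of the Section 5.5 adverse event, mortality and reintervention rates, and no visible text in those subsections brings them back

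*SAP*

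**What the plan says.** Section 5.1.3 of the SAP sets one default population for everything in Section 5.5. It "for each of the cohorts will be among enrolled Subjects (excluding those with a CEC adjudicated 'major' inclusion/exclusion criteria violation or FDA mandated exclusion"). It then leaves any further population detail to the individual subsections. The subsections that report harm say the following:

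- 5.5.4, adverse events: the denominator for each window is "calculated as the number of Subjects remaining in follow-up as of the beginning of the analysis window".
- 5.5.6, all-cause and lesion-related mortality: Kaplan-Meier, where subjects without the event "will be censored at the Subject's last reported contact date" or at the end of the period, whichever is earlier. No population is named.
- 5.5.7, site-reported reinterventions: incidence "will be summarized by analysis time window among those remaining in follow-up", plus Kaplan-Meier for time to first reintervention.
- 5.5.8, stroke and paraparesis/paraplegia: "all Subjects remaining in follow-up will be part of this analysis population".

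Collection is wider than analysis. Section 5.5.4.1.3 says: "All Adverse Events should be reported from enrollment through study completion / discontinuation". Section 5.1.1.2 gives one excluded group its own output: "The 49/53mm Subjects will be summarized separately and followed per the Protocol". Sections 5.1.1.1 and 5.1.1.2 apply the 5.1.3 exclusion to both primary tests as well; each primary population "will be among enrolled Subjects (excluding those with a CEC adjudicated 'major' inclusion/exclusion criteria violation or FDA mandated exclusion"). Section 4.5 gives the grading of eligibility deviations as major or minor to the CEC, and refers to the study protocol for the definitions.

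**The concern.** An eligibility violation does not undo exposure to the procedure or the device. A primary effectiveness test may have reasons to set such subjects aside. A summary of harm normally counts every enrolled subject, because the question is what happened to the people who entered the study.

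Here the safety summaries inherit the exclusion by default. The grading is made after enrollment by the committee that also adjudicates endpoint events, and the visible text does not say that it is done without knowledge of outcome. The cohorts are small and the events of interest are serious and uncommon, so one subject can halve a rate or remove an event from a table. What is at stake is whether the Section 5.5 rates describe all enrolled subjects or a selected part of them.

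**Working it through.** **Step 1: does any visible subsection restore the excluded subjects?** Set each against 5.1.3.

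- 5.5.4 and 5.5.7: remaining in follow-up states who is still at risk when a window opens. It operates within a population and does not define a new one. A major violator who is still followed remains outside, because 5.1.3 has already removed that subject.
- 5.5.6: a censoring rule fixes when observation ends for subjects in the analysis. With no population stated, the 5.1.3 default applies.
- 5.5.8: this subsection speaks of all subjects and uses the term analysis population. Since 5.1.3 sends population details to the subsections, it can be read as an override. It can also be read as another at-risk rule. The text does not settle which.

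So adverse events, mortality and reinterventions lose these subjects on the stated rule; stroke and paraparesis/paraplegia are ambiguous.

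**Step 2: how far can a rate move?** The plan has no figure to reproduce here. Let N be the enrolled subjects, m the number excluded, a the events among those excluded, and b the events among the rest. Then

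all-enrolled rate − reported rate = (a + b)/N − b/(N − m) = (m/N) × [a/m − b/(N − m)].

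The gap is zero if m = 0, and zero on average if excluded subjects have the same event rate as the rest. N is 85 (Zone 2 aneurysm, Primary Enrollment) and 50 (Zone 0/1 aneurysm), from SAP 2.2. The values of m, a and b are assumptions.

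One excluded subject, who has the event:

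- Zone 0/1: 1/50 = 2.0% (two-sided 95% Clopper-Pearson upper bound 10.6%) becomes 0/49 = 0% (upper bound 1 − 0.025^(1/49) = 7.3%).
- Zone 2: 3/85 = 3.5% becomes 2/84 = 2.4%.

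Range, with a rate near 5% in the rest and every excluded subject having the event (the worst case):

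| Cohort | m | Reported | All enrolled | Gap (points) |
|---|---|---|---|---|
| Zone 2 | 1 | 4/84 = 4.8% | 5/85 = 5.9% | 1.1 |
| Zone 2 | 5 | 4/80 = 5.0% | 9/85 = 10.6% | 5.6 |
| Zone 0/1 | 1 | 2/49 = 4.1% | 3/50 = 6.0% | 1.9 |
| Zone 0/1 | 5 | 2/45 = 4.4% | 7/50 = 14.0% | 9.6 |

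**Step 3: the primary tests (secondary point).** The test is one-sided exact at 0.05 (5.3.1), with goals of 60% and 64%. For Zone 0/1 the SAP states a required success rate above 74% with 50 subjects. The exact calculation puts the threshold at 37/50 = 74.0%: P(X ≥ 37 | 50, 0.60) = 0.028 and lower bound 61.9%, while 36/50 gives 0.054 and 59.7% and fails.

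If exclusion is unrelated to outcome, type I error is P(Bin(n, goal) ≥ minimum passing count at that n):

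| Excluded | Zone 0/1 | Zone 2 |
|---|---|---|
| 0 | 37/50: 2.8% | 63/85: 3.1% |
| 1 | 36/49: 3.5% | 62/84: 3.7% |
| 2 | 35/48: 4.4% | 61/83: 4.3% |

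All stay below 5%. It is exceeded only if every excluded subject is a failure: 5.4% and 9.6% (Zone 0/1) or 5.2% and 8.2% (Zone 2) with one and two excluded.

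**The case against.** The strongest objection is that the supplied SAP is incomplete. The text of 5.1.2, 5.4, 5.5.1, 5.5.2, 8.1, 8.2 and Appendix B is not available. Sections 5.5.6 to 5.5.8 say that mortality, additional procedures, stroke and paraparesis/paraplegia also appear among the Success Outcomes, whose population is in 5.1.2. An all-enrolled analysis or a listing may already exist there. This stands, and it limits the point to the Section 5.5 rates. A reader might infer that harm is missing from the trial's safety reporting as a whole; the documents do not support that.

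A reader might also infer that strokes in these subjects are lost. Section 5.5.8 does not support that either, since its wording may already include them.

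Other replies carry less weight. The sentence printed just before 5.1.3 says that other populations may be used, but it permits and does not commit. The DSMB (Section 6.0) reviews reported adverse events with no stated exclusion, but that is monitoring and does not produce the reported rates. Both replies, with collection from enrollment, do show that the gap lies in presentation and not in data capture.

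Finally, the number of major violations is not given and their definition lies in protocol text that is not supplied. If there are none, nothing changes. This also stands.

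**Conclusion.** The point holds for the adverse event, mortality and reintervention rates in Section 5.5. On the visible text, an enrolled subject with a major eligibility violation or an FDA mandated exclusion is outside those rates, and the subsections do not reverse this. For stroke and paraparesis/paraplegia the SAP is ambiguous and needs aligning.

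The size cannot be derived from the documents. With one excluded subject who has the event, the gap is about 1 point in Zone 2 and 2 points in Zone 0/1. The larger gaps shown need several excluded subjects, all with the event. If excluded subjects resemble the rest, the expected rate is unchanged, but their events still go uncounted in these tables.

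A reader might go further and conclude that the exclusion undermines the primary tests. The documents do not support that: the exclusion is pre-specified, no count of major violations is given, and outcome-neutral exclusion of up to two subjects keeps type I error below 5%. For the primary tests it is a possible bias only. The point should be fixed because the remedy is cheap; it does not invalidate the trial.

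**What to change.** **Main change.** In 5.1.3, define the population for adverse events, mortality and reinterventions as all enrolled subjects in each cohort, with no exclusion for eligibility deviations. Keep the existing at-risk denominators and censoring rules. The current population may be shown alongside as supplementary. Align 5.5.8 to the same wording so that stroke and paraparesis/paraplegia are clearly covered.

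**Excluded subjects.** List them with the reason for exclusion and their events, unless 8.2 already provides this. Where an FDA mandated exclusion must stand, summarize those subjects' safety separately, as is already done for the 49/53mm subjects. Leave the 49/53mm, Continued Access and Japan Zone 2 training-case rules as they are.

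**Secondary.** Keep the pre-specified primary population. Add a sensitivity analysis of each primary composite with major violators kept in, unless 5.5.1 already provides it; 5.3.1 describes those analyses as addressing missing data.

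**Cost.** SAP wording and a little extra output for each cohort, with no new patients or data. The downside is that the figures may be slightly less favourable.
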